Spontaneous Void Requirements for Patients Undergoing Ambulatory Anorectal Surgery**TABLE OF CONTENTS**

OBJECTIVE	2
BACKGROUND & RESEARCH SIGNIFICANCE	2-3
HYPOTHESIS	3
PRIMARY & SECONDARY OBJECTIVES	3
STUDY PLAN & PROCEDURES	3
INCLUSION/EXCLUSION CRITERIA	3
MEASUREMENT OF STUDY VARIABLES	4-5
STATISTICAL ANALYSIS	5
FUNDING	6
BIBLIOGRAPHY	6

Objective

Urinary retention is a common complication following anorectal surgery and is thought to be multifactorial. Some researchers explain post-operative urinary retention as a consequence of long acting analgesics which dampen the ability for bladder fullness¹. Others point to irritation to pelvic nerves that function with micturition thus blunting pain evoked reflexes^{2,3}. Modifiable factors that have been found to play a role in contributing to post-operative urinary retention include the use of intravenous fluids over one liter during surgery, and administration of local analgesics. Local analgesics provide significant acute pain relief, but contribute to the theory of blunted pain reflexes. Inadequate pain control increases likelihood of urinary retention through inability of perineal relaxation. A balance must be maintained between adequate pain control and interfering with the micturition reflex. Non-modifiable risk factors include age, female sex, the presence of diabetes mellitus, and specific surgical procedure⁴.

Complications of post-operative urinary retention include an increase in urinary tract infections, hospital readmission, damage to detrusor contractility, and for the elderly increased confusion and delirium⁵. The rate of urinary retention post anorectal surgery is between 16-20%. The incidence of urinary retention following high-risk ambulatory surgery is stated to be 5%. The objective of this study is to assess if not requiring patients to spontaneous void prior to discharge from the post-anesthesia care unit (PACU) will result in shorter lengths of stay in the post-anesthesia care unit without increasing hospital readmissions or emergency room visits.

Background & Research Significance

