1. To compare readmission and complications rates between patients who are required to void post anorectal surgeries to those who are sent home without voiding spontaneously.
2. To compare the rates of emergency room visit between patients who are required to void post anorectal surgeries to those who are sent home without voiding spontaneously.

Secondary Objectives:

1. To compare PACU times for patients who are required to void post anorectal surgeries to those who are sent home without voiding spontaneously.
2. To compare total hospital costs for patients who are required to void post anorectal surgeries to those who are sent home without voiding spontaneously.

Study Plan and Procedures

This study will be a prospective clinical trial, in which 100 anorectal surgery patients will be randomly assigned to a control (spontaneous void) or experimental (no void) group.

Randomization will be done using the free software provided by www.randomizer.org.

“Spontaneous void” group will include 50 patients who will required to void spontaneously after anorectal surgeries. On the other hand “no void” group will be 50 patients who will be discharged home from the PACU once they meet ambulatory surgery center discharge criteria per hospital guidelines. Patients requiring anorectal surgeries will be consented to take part in the study during the preoperative outpatient office visit. A post op phone call will be made by designated study personnel to participants on post-op day 30 using a study questionnaire to assess re-admission and emergency room visits.

Inclusion Criteria:

1. Age 18-80 years old
2. Patients undergoing hemorrhoidectomy, fistulotomy or anal condyloma excision.

Exclusion Criteria:

1. Age <18 yo or >80 yo
2. Prisoners
3. Pregnant Women

4. Unable or unwilling to follow the study protocol or any reason the research team believes the subject is not an appropriate candidate for this study

Measurements of Study Variables

To achieve the study goals, the following data will be collected:

Pre-operative Data:

1. Demographics: age, sex, height, weight, BMI, race
2. Insurance type
3. Past medical history
4. Diabetes history
5. Hemoglobin A1C
6. Coronary artery disease
7. Chronic obstructive pulmonary disease
8. Inflammatory bowel disease
9. Diagnosis of cancer
10. Renal dysfunction
11. Past surgical history
12. Steroid use
13. Immunosuppression
14. Smoking history
15. Substance abuse
16. Diagnosis
17. ASA class
18. Elixhauser comorbidity index

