19. Hospital Cost

Post-Operative:

1. Procedure CPT
2. Where procedure took place
3. Date of procedure
4. Length of procedure
5. Estimated blood loss
6. Reoperation during index admission
7. Diagnosis of Urinary retention
8. Post-operative complications
9. Length of hospital stay in days
10. ICU admission
11. ED visit
12. Readmission
13. Interval to last follow up in days
14. Blood transfusion requirements
15. Total IV fluids received

16. Total pain medicine received
 17. Hospital Cost

Post-Operative Phone Call:

1. Emergency department visit, urgent care visit, or admission outside of The Ohio State University Wexner Medical Center within 30 days post-operative
2. Reason for admission, emergency department visit, or urgent care visit

Schedule of Events

	Pre-Operative Appointment	30 Days Post-Operative
Assess Eligibility Criteria	X	
Informed Consent	X	
Pre-Op Data	X	
Post-Op Phone Call		X
Post-Op Data		X

Statistical Analysis

Data will be expressed using means +/- standard deviations in addition to sample size (n) and percentages. Further statistical analysis will include Students t test for quantitative variables and chi squared test for comparisons of qualitative variables. A p value <0.05 will be used for statistical significance.

Sample Size Calculation:

Power	N1	N2	μ_1	μ_2	$\mu_1 - \mu_2$	σ_1	σ_2	Alpha	Beta
0.80000	50	50	210.0	129.1	80.9	100.0	175.0	0.050	0.20000
0.80000	75	75	210.0	144.3	65.7	100.0	175.0	0.050	0.20000
0.80000	100	100	210.0	153.2	56.8	100.0	175.0	0.050	0.20000

Report Definitions

Power is the probability of rejecting a false null hypothesis.

N1 and N2 are the number of items sampled from each population.

μ_1 and μ_2 are the assumed population means for power and sample size calculations.

$\mu_1 - \mu_2$ is the difference between population means at which power and sample size calculations are made.

σ_1 and σ_2 are the assumed population standard deviations for groups 1 and 2, respectively.

Alpha is the probability of rejecting a true null hypothesis.

Beta is the probability of accepting a false null hypothesis.

Summary Statements

Group sample sizes of 50 and 50 are needed to achieve 80.000% power to reject the null hypothesis of equal means when the population mean difference is $\mu_1 - \mu_2 = 210.0 - 129.1 = 80.9$ with standard deviations of 100.0 for group 1 and 175.0 for group 2, and with a significance level (alpha) of 0.050 using a two-sided two-sample unequal-variance t-test.

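### PACU time is compared by an unadjusted t test; prespecifying adjustment for planned procedure and age would be a cheap improvement, with a gain that depends on an unknown R²

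*Combined protocol and SAP*

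**What the plan says.** The Statistical Analysis section states: "Further statistical analysis will include Students t test for quantitative variables and chi squared test for comparisons of qualitative variables". It names no regression model, covariate or stratified analysis. Study Plan and Procedures identifies the randomisation software and describes no stratification.

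PACU time is the first secondary objective ("To compare PACU times for patients who are required to void post anorectal surgeries"). The Sample Size Calculation concerns a difference in means, with first row "210.0 129.1 80.9" and SDs of 100 and 175. It is sized "with a significance level (alpha) of 0.050 using a two-sided two-sample unequal-variance t-test". The table names neither endpoint nor unit; I take it to be PACU minutes.

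The Objective section says: "Non-modifiable risk factors include age, female sex, the presence of diabetes mellitus, and specific surgical procedure". The risk in question is post-operative urinary retention. Age is on the pre-operative data list. Procedure (as a CPT code) and "Where procedure took place" are on the post-operative list. The inclusion criteria admit three procedure types.

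**The concern.** The trial has 50 patients per arm, 80% power for a large difference (80.9 / 210 = 38.5% of the larger mean), and no stated allowance for dropout. Baseline variables that predict PACU time could narrow its confidence interval without adding patients. They would also correct for chance imbalance between the arms, as far as a linear model fits. The protocol suggests a mechanism: its Background reports that requiring a void prolongs PACU stay, so factors that delay voiding could lengthen the stay of patients who must void. If adjustment is wanted, the covariates have to be fixed beforehand, because choosing them after seeing the data would weaken the result.

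**Working it through.** **Inputs.** From the Sample Size Calculation: 50 per arm, difference 80.9, SDs 100 and 175, two-sided alpha 0.05. Assumed: R², the share of within-arm variance in PACU time explained by the covariates. Covariate terms k = 3 (age, plus two indicators for three procedure types).

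**Step 1. Reproduce the plan's figure.**

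- SE = √(100²/50 + 175²/50) = √(200 + 612.5) = 28.50.
- Satterthwaite df = 812.5² / [(200² + 612.5²)/49] = 77.9.
- Noncentrality = 80.9 / 28.50 = 2.84.
- Power from the noncentral t is 80.0%, as stated. The equal-variance test gives 80.2%, so the plan's mixture of Student and unequal-variance wording hardly matters at equal n.

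**Step 2. Three-term adjustment, closed form.** The residual variance is multiplied by (1 − R²). Chance covariate imbalance inflates it by (2n − 3)/(2n − k − 3) = 97/94, and 3 df are lost (74.9 remain). So SE = 28.50 × √[(1 − R²) × 97/94].

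| Assumed R² | SE | Power | Change from 80.0% |
|---|---|---|---|
| 0 | 28.96 | 78.8% | −1.3 |
| 0.05 | 28.22 | 80.8% | +0.7 |
| 0.10 | 27.47 | 82.8% | +2.8 |
| 0.20 | 25.90 | 86.9% | +6.9 |

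Break-even is at R² of about 0.03.

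**Step 3. Simulate the same model with HC2 standard errors.** I used 20,000 runs per R², normal errors, three equally common procedures, and age and one procedure indicator equally prognostic. Power was 78.9%, 80.8%, 83.1% and 86.6% at the four R² values, against 80.1%, 79.9%, 80.5% and 80.0% for Welch in the same runs. With no true difference (R² = 0.10), HC2 rejected in 5.3% of runs and Welch in 5.2%. A separate simulation of a three-term HC2 model gave about −1, 0, +1 to 2, and +6 to 7 points, with break-even near R² = 0.05. The covariate mix and error distribution are assumed, so I carry the more cautious set forward.

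**Step 4. Why the covariate set should be short.** Six terms (age, sex, diabetes, two procedure indicators, hospital) change the factor to 97/91 and cost 6 df. The closed form then gives 77.4%, 79.5%, 81.6% and 85.8% at R² = 0, 0.05, 0.10 and 0.20, with break-even near 0.064. With HC3 standard errors, which are more conservative, simulated power is about 75%, 76%, 79% and 83%. That model loses power at R² of about 0.10 or below.

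**Step 5. If the covariates matter only where a void is required.** Suppose group 1, with mean 210 and SD 100, is the void arm (inferred; the table does not label the groups). It contributes 100²/(100² + 175²) = 10000/40625 = 24.6% of the variance of the difference. An R² of 0.30 confined to that arm removes at most 0.30 × 24.6% = 7.4% of the total. Simulated as in Step 3, this gave 79.8% power adjusted and 79.6% unadjusted, so no material gain.

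**The case against.** The strongest reply is that nothing is broken. Randomisation makes the unadjusted comparison valid, and the stated 80% power belongs to that test and reproduces. The risk factors are named for urinary retention, and no section says that they predict PACU time. No R² is given, and the mechanism works mainly in the arm that contributes less of the variance. All of this stands. It rules out calling the plan wrong and rules out promising a gain. It does not rule out a short prespecified model, whose worst-case loss is about one point.

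A reader might infer three stronger things that the documents do not support.

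- **That the precision is free.** Multiplying both SDs by √(1 − R²) and stopping there gives power of 82%, 84%, 88% and 92% at R² = 0.05, 0.10, 0.20 and 0.30. That ignores the lost degrees of freedom, chance covariate imbalance and the behaviour of robust standard errors.
- **That hospital must be a strong covariate.** The two hospitals appear in the Background as current practice and as the setting of a retrospective review. The protocol does not say that both enrol in the trial. The difference it documents between them is the void policy, which the trial itself assigns.
- **That cost would gain too.** Cost is a secondary objective ("To compare total hospital costs for patients who are required to void post anorectal surgeries"), but no SD, effect or R² for it is given, so no gain can be calculated.

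**Conclusion.** The point holds as a cheap improvement and not as an error. With planned procedure and age in the model, 50 per arm and HC2 standard errors, power for 80.9 changes from about 80% by roughly −1 point at R² = 0, 0 at 0.05, +1 to 2 at 0.10, and +6 to 7 at 0.20. This rests on an assumed R², on reading the sizing table as PACU minutes, on the planned SDs of 100 and 175, and on covariates that predict similarly in both arms. If they predict only in the void arm, expect little or no gain. The planned sample size stands for the unadjusted test.

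**What to change.** Add to Statistical Analysis, for PACU time only: a linear model of the outcome on assigned arm, planned procedure type and age, fixed before any outcome data are seen. Include planned site only if both hospitals enrol. Use HC2 heteroscedasticity-robust standard errors, because the plan assumes unequal SDs, and report the unadjusted Welch difference alongside.

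Procedure CPT and location sit on the post-operative list, so record the planned procedure (and planned site, if used) as known before randomisation, and adjust for those. PACU time itself is not on the list in Measurements of Study Variables and needs to be added for either analysis.

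The cost is a few sentences and one regression. No patients are added, and the only change to covariate collection is to record the planned values beforehand. The statistical price is three degrees of freedom, or about one point of power if the covariates predict nothing.
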